2. ABSTRACT

Introduction: According to the World Health Organization (WHO), obesity is an abnormal or excessive accumulation of fat, which could affect human health. Mexico has one of the highest prevalence of obesity, reported by 32.4% of people over 20 years old, according to National Health and Nutrition Examination Survey (ENSANUT, Encuesta Nacional de Salud y Nutrición 2012). This implies that 22 millions of Mexicans have obesity. Additionally, the prevalence of obesity class III (defined as a body mass index greater than 40 kg/m^2) is 1.8% (IC95% 1.5-2.1%) in males and 4.1% (3.7%-4.5%) in females.

The Mexican Social Security Institute (IMSS, Instituto Mexicano del Seguro Social) (that has one of the widest health coverages in the country) has reported a prevalence of obesity on its affiliates up to 74.4%, but only 50% had received clinical care for weight control (for example, diet or physical activity recommendations). In a recent article published by Barrera-Cruz et al. it is estimated that this disease reduces life expectancy from 6 to 20 years, being responsible for 2.8 million deaths per year in our country. In addition, it is estimated that it generates an annual cost of 3,500 million dollars for direct and indirect costs.

Since 2008, a multidisciplinary clinic focused on obesity treatment and related comorbidities has been organized at the Hospital de Especialidades of Centro Médico Nacional Siglo XXI. Currently, the "Obesity Clinic" attends a 400-patient population, of which 150 patients have undergone bariatric surgery (gastric bypass or gastric sleeve) and 250 patients are on waiting list and preparation for this procedure. According to previous data (not yet published) the mean age of these patients is 41 ± 9 years, 46% have pre-diabetes or type 2 diabetes mellitus, 66% has hypertension and 33% has dyslipidemia (hypertriglyceridemia, hypoalphalipoproteinemia or both). The management of glucose alterations on this unit is done with personalized diets supervised by the Nutrition Service of the Obesity Clinic and with the use of metformin at doses greater than 2 g/day and/or basal insulin at doses of 0.5 to 1 U/kg of patient's weight.

Recently, a group of drugs known as inhibitors of sodium-glucose transporter protein 2 (iSGLT2) has been approved for T2D treatment. These low-affinity and high-capacity transporter proteins are found at proximal convoluted tubules and are responsible for glucose re-absorption; therefore, its inhibition induces glycosuria and subsequently a decrease of plasmatic glucose. Dapagliflozin is a selective iSGLT2 with a sustained effect on the reduction of glycated hemoglobin (HbA1c) at 0.4 to 0.8%. Additionally, due to the induction of glycosuria up to 20-85 g/day, it has been calculated that its use induces a caloric deficit at 80 to 340 kcal/day. This has been observed in patients with T2D in which induces a weight loss of 2 to 3 kg and in combination with metformin even a weight loss up to 5.07 kg (-6.21 to 3.93 kg) without regain (at least for 2 years) as

previously demonstrated. Furthermore, it decreases systolic blood pressure (4-5 mmHg), increases concentration of HDL cholesterol (1.8 to 4.4%) and decreases triglycerides concentration (2.4 to 6.2%). Due its mechanism of action is independent of insulin production; there exists a possibility of using dapagliflozin in patients with prediabetes or even on other types of diabetes. Regarding safety considerations, main adverse effects related to its use are genitourinary infections and it has been demonstrated that it does not induces kidney injury.

A previous study by Bolinder et al. that included 182 patients with T2D inadequately controlled with metformin, assessed the effect of dapagliflozin 10 mg in weight loss after 24 weeks of treatment and compared it to placebo. They found a decrease of 2.08 kg (2.8 to 1.31 kg, $p<0.001$), decrease in waist circumference of 1.52 cm (2.74 to 0.31, $p=0.014$), decrease in total fat mass assessed with densitometry (DEXA) of 1.48 kg (2.22 to 0.74, $p=0.001$), decrease of visceral fat mass of 258.4 cm³ (448.1 to 68.6, $p=0.008$) and decrease of subcutaneous fat of 184.9 cm³ (359.7 to 10.1, $p=0.03$). However, those studies on weight are performed in patients with obesity class I or II and there is a lack of information on inflammatory markers after dapagliflozin treatment.

Primary objective: To determine if combined treatment with dapagliflozin and metformin is more effective than monotherapy with metformin for weight loss and assess its effects on waist circumference, triglycerides, blood pressure and inflammatory cytokines (resistin, adiponectin, interleukin-6 and interleukin-10) in prediabetic and diabetic patients with obesity class III.

Secondary objective: To determine the effect of combined treatment with dapagliflozin and metformin in comparison with monotherapy with metformin on serum concentrations of glucagon, ghrelin and insulin.

Patients, material and methods: The protocol includes patients with previous or recently diagnosed diabetes or prediabetes from the Obesity Clinic of CMN SXXI from July 2018 to August 2023 age 18 to 60 years old, both male or female and not treated with insulin. Patients requiring initial treatment with insulin, with obesity secondary to other comorbidities and patients who do not wish to enter the study or not provide their informed consent will be excluded. Patient's data that during the study are advised to undergo bariatric surgery will be used until the moment of surgery. Other treatments will be adequately recorded. Patients will be randomized by computer software and assigned in a group treated with metformin (>2 g/day, group 1) or with metformin (>2 g/day) and dapagliflozin 10 mg (group 2). All patients will receive dietary treatment and follow-up by the Nutrition service during the study. Anthropometric and biochemical variables will be recorded at the beginning and at months 3, 6 and 12. Adherence to treatment will be assessed, defined by consumption of at least 90% of provided pills. The adverse events will be recorded since the beginning of study and will be ranked according to the CTCAE lists (Common terminology criteria for adverse events version 4.03). An intention-to-treat analysis will be performed in case of patients that require treatment with insulin.

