The Mexican Social Security Institute (IMSS) has the broader coverage of health of the country. According to ENSANUT 2012, 74.4% of its beneficiaries are obese and it is estimated that only 50% receive medical attention focused on weight control (e.g. diet or physical activity recommendations). Considering the current increase in the prevalence of obesity and an imperious need of reducing the prevalence of co-morbidities and high mortality rate associated with this disease, since 2008 the Hospital de Especialidades from the Centro Medico Nacional Siglo XXI organized a multidisciplinary team composed by members from departments of Endocrinology, Clinical Nutrition, Bariatric Surgery, Psychiatry and Internal Medicine, under the name of "Obesity Clinic".

The requirements for admission are a BMI greater than 35 kg/m² with a major comorbidity (diabetes, hypertension, dyslipidemia or sleep apnea syndrome) or obesity class III. Patients are initially evaluated by nutritionists authorized to assess anthropometric measures, who also adjust diet based on weight and initial consumption of calories and evaluate patients monthly recording weight, waist and hip circumference, percentage of adherence to diet and amount of physical exercise per week (measured in minutes per week). At the same time, the endocrinologists perform clinical assessment and laboratory tests for detection and control of comorbidities such as altered metabolism of glucose (Type 2 diabetes [T2D] or pre-diabetes), hypertension (HTN) and dyslipidemia and request assessment and treatment of other specialists if necessary. Meanwhile, psychiatrists perform tests for detection and treatment of anxiety disorders or depression, eating disorders, personality disorders and other psychiatric comorbidities that could influence negatively on the management of patients and finally, once the patients lost 10% of excess of weight, they become candidates for bariatric surgery (laparoscopic Roux-Y bypass or gastric sleeve, depending on the evaluation of surgeons).

Several studies support that weight reduction before surgery decreases surgical risk and improves time to recovery. It has been observed that patients with super-obesity have a higher incidence of complications during bariatric surgery associated with increased technical difficulties (for example an increased liver volume due to steatosis), increased anesthetic risk and risk of treatment failure.

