Different studies have reported a modest decrease in weight or stability compared with other hypoglycemic medications [46]. Hermann et al. were the first to describe the body weight effects of metformin [47]. In 1991 they studied 25 patients with a mean age of 59 years (range 36-69 years) with an average weight of 76.4 kg (63-97 kg) for women and 77.4 kg (64.5-92 kg) for men previously treated with glyburide. In this group, they observed a decrease of -2.64 kg of total weight (95% CI -4.23 to -1.05 kg) after one year of treatment. Subsequently Stumvoll et al. conducted a study with 10 patients with T2D (6 men and 4 women), aged 58 ± 9 years and average BMI of 32.1 ± 3.2 kg/m² to those treated with initial doses of metformin 850 mg increments every two weeks to 2550 mg (850 mg three times a day) [48]. After 16 weeks observed a total weight loss of -2.7 ± 1.3 kg (95.1 ± 14.9 vs. initial 92.4 ± 14.5 kg end, $p < 0.001$) and -2.4 ± 2.2 kg of fat mass, determined by bioimpedance (initial 31.2 ± 11.4 vs. 28.9 ± 10.1 kg end, $p = 0.02$) [48]. That same year, DeFronzo et al. conducted a study to compare the metabolic effects of metformin, glyburide, and the combination of both. In that study the group with metformin (n=210 patients, average age 55 ± 1 years, mean BMI 29.4 ± 0.3 kg/m²) reported a loss of -3.8 ± 0.2 kg, compared with less weight loss observed in the group with glyburide or the weight gain observed in the group with combination therapy for 29 weeks [49].

Moreover, Mogul et al. conducted a retrospective analysis of 30 non-diabetic women who previously tried to lose weight with diet and exercise and grouped them into two categories of BMI: 25 to 32.9 kg/m² (group 1) and 33 to 41.7 kg/m² (group 2). In addition to a hypocaloric diet, they received a dose of 1500 mg and 2000 mg metformin, respectively. In group 1, a loss of 3.47 kg (SE, standard error 0.68), 6.41 kg (0.72) and 8.06 kg (0.96) at 3, 6 and 12 months of treatment

was observed and in group 2 a weight loss of 4.4 kg (0.8), 9.7 kg (2.3) 15.1 (3.3) kg was observed at those times. In this study, 96% of patients achieved a loss of more than 5% of body weight at 6 months and 81% lost more than 10% of weight at 12 months [50].

Weight loss associated with dapagliflozin

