- 4) Patients will be randomized by a random numbers system generated with a computational software and will be assigned to a group: 1) metformin (2 g/day) or 2) metformin (2 g/day) and dapagliflozin 10 mg. All patients will receive dietary treatment and follow-up during the study by Nutrition service. Dietary treatment is individualized, as it is based on the initial weight of the patient and their eating habits at the time of valuation. It is expected that dietary treatment does not influence the results because all patients will undergo diet and those with little attachment (defined as failure to comply with at least 80% of the prescribed diet) are discharged of the surgical protocol. The Nutrition service calculates the percentage of adherence to diet.
- 5) Once assigned to the corresponding group, patients will receive an identification code that will be retained throughout the study. One of the researchers not directly involved in patient care, will assign tablets needed for daily intake for a month and then the number of tablets required for 3 months in a sealed envelope.
- 6) A run-in period will be used to assess tolerance to treatments. This period will be for a month. At this time patients will be advised of a possible increase on urea and will be instructed in the relevance of increasing fluid intake.
- 7) The anthropometrical and biochemical variables will be recorded at baseline and at 1, 3, 6 and 12 months (Appendix 2. Data Collection Sheet). A clinical nutritionist accredited as Level 1 Anthropometrist by the International Society for the Advancement of Kinanthropometry (ISAK) will assess the weight on a scale with a

maximum capacity of 300 kg and precision of 100 g; height using an stadiometer, and waist circumference using a fiberglass tape, according to the manual of procedures for nutrition projects of the Centro de Investigación en Nutrición y Salud de Instituto Nacional de Salud Pública [86], and also in accordance with the procedures manual for the assessment of clinical and anthropometrical measurements in the adult and elderly of the Ministry of Health [87] (Appendix 3. Clinical and anthropometric measurements).

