6. Use of drugs for weight control.
7. Untreated or uncontrolled hypothyroidism (defined through TSH higher than 4.2 μ U/ml)
8. Pregnant or lactating mother.
9. Tobacco use (in the last month)
10. Current use of steroids or nonsteroidal anti-inflammatory drugs

Withdrawal criteria

1. Becoming pregnant during the study
2. Tobacco use
3. Use of steroids during the study

Sample size

Weight loss after dapagliflozin treatment has not been previously used as primary outcome in randomized controlled trials (RCT) of patients with prediabetes or diabetes and grade III obesity. Zhang et al. performed a meta-analysis that included seven RCTs evaluating the effect of metformin combined with SGLT2-inhibitors (dapagliflozin 10 mg/day, canagliflozin 300 mg/day, empagliflozin 25 mg/day, or ipragliflozin 300 mg/day) vs. metformin (at doses of 1.5 to 3 g/day) with placebo on HbA1c; fasting plasma glucose; and body weight over 24 weeks, 1 year, and 2 years. The total sample was 2847 patients with a mean BMI of 31.7 ± 4.9 kg/m². After a year of treatment, the placebo-metformin control group showed a reduction in body weight of 1.1 ± 3.39 kg, whereas the SGLT-2 inhibitor-metformin group showed a 3.6 ± 4.22 kg reduction with a mean difference of -2.6 kg (-3.17 to -2.03 kg), $p < 0.0000$. Using these data, we calculated a sample size using a mean difference formula. With a power of 80% (alpha level of 0.05) in a two-sided T-test, the sample size required is 90 patients: 45 patients in the M group and 45 patients in the D/M group. The final sample size required is 108 patients: 54 patients in metformin and 54 patients in the dapagliflozin group, allowing for a 20% dropout rate.

Variable definition

Variable name	Variable Type	Scale	Conceptual definition	Operational definition	Units
INDEPENDENT VARIABLES					

Type of treatment	Qualitative, dichotomic	Nominal	Metformin is a biguanide with effect in cyclic AMP kinase that diminishes insulin resistance. Diabetes treatment guidelines consider it as the first line therapy. Dapagliflozin is an SGLT2 inhibitor that induces glycosuria and has been approved for monotherapy in patients with metformin intolerance and also as a second or third line therapy for diabetes.	Use of metformin 2 grams per day or use of metformin 2 grams per day in combination with 10 mg of dapagliflozin.	0 = metformin, 1 = metformin/dapagliflozin
-------------------	-------------------------	---------	--	--	---

DEMOGRAPHIC VARIABLES

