Interleukine 10 (IL-10)	Quantitative continuous	Ratio	Anti-inflammatory cytokine related to the development of atherosclerosis	Concentration determined using the method ELISA.	pg/ml
Ghrelin	Quantitative continuous	Ratio	Hormone secreted in the gastric fundus that induces appetite.	Concentration determined using the method ELISA.	pg/ml

Glucagon	Quantitative continuous	Ratio	Hormone produced by pancreatic alpha cells that counteracts the effects of insulin.	Concentration determined using the method ELISA.	ng/ml
----------	-------------------------	-------	---	--	-------

Statistical analysis: Quantitative variables were described using measures of central tendency and dispersion according to the data distributions. Qualitative variables were described using frequencies or percentages. The Shapiro-Wilk test was used to establish normality in the distribution of quantitative variables. Because information on the different quantitative variables was available up to different time periods, a mixed model analysis was performed using the restricted maximum likelihood (REML) method, as well as a mixed model considering the fixed effects of assigned treatment, sex, and prediabetes or diabetes status, and the random effects of variability in weight loss over time. Comparisons between groups were analyzed using Sidak's post-hoc test. Pearson's chi-square test or Fisher's exact test were used to evaluate the association between qualitative variables. Statistical significance was defined as a $p < 0.05$. Data analysis was performed using SPSS version 17.0 and STATA version 11.0.

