11. RESOURCES AND ENVIRONMENT

Human resources. All the investigators participating in this study have expertise in clinical trials, they are trained in the management of the patients attending to the clinic and they are authorized to perform and handle blood samples and patient data.

The investigator group includes one attending physician registered in the obesity clinic in the Endocrinology department, which will also be in charge of this protocol as part of the work to achieve his Doctors degree in Science (D.Sc.); other members of the group are two attending general endocrinologists with experience in clinical investigation in obesity and two other endocrinologists from the Experimental Endocrinology Unit which constitutes the laboratory area of the Endocrinology department. These endocrinologists can perform the laboratory techniques required for this protocol and one of them has been previously involved in protocols with pharmaceutical companies.

Material resources. The investigation unit and the endocrinology department have the necessary equipment required for the procedures. We will apply for financing for the purchase of the ELISA kits as well as for some of the supplies required for the protocol.

Feasibility. According to the large number of patients existing in the Obesity Clinic that are waiting for bariatric surgery and the frequency of metabolic disturbances found in the extremely obese, we consider that the number of patients required for the study is feasible.

The clinical and laboratory investigators involved in this protocol have the necessary expertise for the management of patients with extreme obesity, taking blood samples and information gathering. The Investigation Unit has ample experience in the management of biological samples and analysis with ELISA. They have also performed studies in the field of immunoendocrinology.

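### The weight model omits how long, and with what weight change, each patient had been in the clinic's diet programme before randomisation; the cost is precision, not bias

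*Combined protocol and SAP*

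**What the plan says.** Section 8 (Study Population) draws the sample from Obesity Clinic patients who are being prepared for bariatric surgery. The Abstract describes the pool: "250 patients are on waiting list and preparation for this procedure". The Feasibility paragraph of section 11 relies on the "large number of patients existing in the Obesity Clinic that are waiting for bariatric surgery". Section 7 adds that up to 10 new patients a month are assessed for admission.

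Clinic care begins at admission. Section 7 says the nutritionists adjust the diet and "evaluate patients monthly recording weight, waist and hip circumference, percentage of adherence to diet and amount of physical exercise per week". The selection criteria in section 8 set no minimum, maximum or fixed interval between clinic entry and randomisation, and no stratification is stated.

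On diet, Workplan item 4 says: "It is expected that dietary treatment does not influence the results because all patients will undergo diet". The Statistical analysis paragraph specifies "a mixed model considering the fixed effects of assigned treatment, sex, and prediabetes or diabetes status", plus random effects for weight loss over time. The data sheet in Appendix 2 has an inclusion date but no field for clinic-entry date or clinic-entry weight.

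**The concern.** A patient on the first day of a supervised diet and a patient several months into it are likely to lose different amounts over the next year. The diet argument in Workplan item 4 covers who receives diet. It says nothing about how long each patient has already had it.

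If the sample mixes the two kinds of patient and the model cannot tell them apart, the difference between them goes into residual variance. The treatment contrast is then estimated less precisely than the clinic's own records would allow. A reader of the results also could not see whether prior weight loss was similar in the two arms.

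**Working it through.** **Plan's own figure.** The inputs from Sample size (section 8) are a control change of 1.1 kg (SD 3.39), a combination change of 3.6 kg (SD 4.22), two-sided alpha 0.05 and power 80%. The difference between arm means is 3.6 − 1.1 = 2.5 kg; the same paragraph also gives a mean difference of 2.6 kg. With 2.5 kg and SD 4.22 in both arms:

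n per arm = 2 × (1.96 + 0.84)² × 4.22² / 2.5² ≈ 44.7, so 45 per arm.

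This reproduces the plan: "With a power of 80% (alpha level of 0.05) in a two-sided T-test, the sample size required is 90 patients". By the exact t-test, power at 45 per arm is 79.4%.

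**Two quantities the documents do not give.** Let p be the share of established patients and D the gap in later weight loss between new and established patients. I take p = 0.5 as an assumption.

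**A range for D.** The only proxy is the retrospective series in section 7 of 30 non-diabetic women on diet plus metformin. Its heavier group had "a weight loss of 4.4 kg (0.8), 9.7 kg (2.3) 15.1 (3.3) kg" at 3, 6 and 12 months.

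- Heavier group: months 0-6, 9.7 kg; months 6-12, 15.1 − 9.7 = 5.4 kg; gap 4.3 kg.
- Lighter group: months 0-6, 6.41 kg; months 6-12, 8.06 − 6.41 = 1.65 kg; gap 4.76 kg.
- Three-month windows (0-3 v 3-6) show little slowing: 4.4 v 5.3 kg in the heavier group, 3.47 v 2.94 kg in the lighter.

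Trial follow-up is 12 months. For a patient s months into the programme, D is the loss in months 0 to s minus the loss in months 12 to 12 + s. Assume loss after month 12 is no faster than in months 6-12. At s = 6, D is then at least 4.3-4.8 kg. At s = 3, D is at least 4.4 − 5.4/2 = 1.7 kg (heavier) or 3.47 − 1.65/2 = 2.6 kg (lighter). I carry D = 2 and D = 4.5 kg as illustrations.

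**Effect on SD and power** (45 per arm, 2.5 kg, exact t-test). The mix contributes variance p(1 − p)D² = 0.25D².

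| | D = 2 kg | D = 4.5 kg |
|---|---|---|
| If 4.22 excludes the mix: unadjusted SD = √(4.22² + 0.25D²) | 4.34 | 4.78 |
| Power, unadjusted | 77.2% | 68.9% |
| Standard error cut by adjusting, 1 − 4.22/SD | 2.7% | 11.8% |
| If 4.22 includes the mix: adjusted SD = √(4.22² − 0.25D²) | 4.10 | 3.57 |
| Power, adjusted | 81.6% | 90.7% |
| Standard error cut by adjusting, 1 − SD/4.22 | 2.8% | 15.4% |

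Estimating the covariate effect gives back a little of each cut, so about 3% and 11-15% are fair summaries. In the first case adjustment restores power to about 79%. In the second, unadjusted power is already at that level.

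**Bias check.** In 10,000 simulated trials per setting with p = 0.5 and D = 4.3 kg, the unadjusted analysis had type I error 5.0% and a mean estimate of 2.50 kg. Its standard error was 1.00 kg, against 0.90 kg adjusted; power was 69.4% against 78.8%.

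**Chance imbalance is the same quantity as the extra variance.** Its SD is D√(2p(1 − p)/45), which is 0.47 kg at D = 4.5. The within-group standard error is 4.22 × √(2/45) = 0.89 kg. Combined, √(0.89² + 0.47²) = 1.01 kg, which equals 4.78 × √(2/45).

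**The case against.** **The comparison is valid without these covariates.** This stands. A reader might infer that chance imbalance in programme time could shift the result by a large part of 2.5 kg, as a harm on top of the extra variance. The documents do not support that. The 95% limit of the imbalance at D = 4.5 kg is 1.96 × 0.47 = 0.93 kg, but randomisation already puts this into the standard error and confidence interval. Counting it again beside the variance is double counting.

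**The established share is unknown.** This stands too. The Abstract sentence describes the clinic, not the trial sample, and Workplan item 1 samples patients who attend during the study period. At up to 10 new assessments a month, with 46% having prediabetes or diabetes (a figure from operated patients), the Abstract's window of July 2018 to August 2023 gives up to 62 × 10 × 0.46 ≈ 285 new candidates. Section 8's window of December 2016 to October 2018 gives up to 23 × 10 × 0.46 ≈ 106. Both are before other exclusions, so new patients could be the majority. Prior weight loss is likewise an inference: section 3 says many clinic patients fail to lose weight.

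**The proxy for D is weak.** Its patients were non-diabetic and took metformin along with the diet, so the two effects cannot be separated. They lost 8-15 kg in a year, whereas in the planning source "the placebo-metformin control group showed a reduction in body weight of 1.1 ± 3.39 kg". D could be well below 4.5 kg.

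**The power loss depends on the SD chosen.** With the pooled SD, √((3.39² + 4.22²)/2) = 3.83, unadjusted power at D = 4.3 kg is 77.1% (normal approximation). With patients leaving early for surgery, the gain from adjustment would be smaller.

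**Early exit.** A reader might also infer that loss before randomisation decides who leaves for surgery. That holds only if the surgical threshold is counted from clinic entry, which the documents do not settle, so I do not rely on it.

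None of this answers the narrower point that a probable prognostic factor, recorded by the clinic, is neither collected nor modelled, and that the diet argument does not reach it.

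**Conclusion.** The point holds as a matter of precision. The documents show that clinic care can precede randomisation, that nothing fixes by how long, and that neither the model nor the data sheet records it. They do not show bias, inflated type I error or an invalid primary comparison.

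The size is not determinable from the documents. It ranges from negligible (about 3% of the standard error, about 2 points of power, at D = 2 kg) to moderate (11-15%, and about 10-11 points of power, at D = 4.5 kg). These figures assume half the sample are established patients, 45 analysed per arm, a 2.5 kg effect and a simple new/established split. Whether the planning SD already contains this variation decides whether adjustment recovers lost power or adds to the planned power. It is an inexpensive improvement worth making.

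**What to change.** - Take each patient's clinic-entry date and entry weight from existing clinic records, and add both fields to the Appendix 2 data sheet.
- Tabulate by arm the months in programme at randomisation and the percent weight change from clinic entry to randomisation.
- Add these two variables as baseline covariates in the mixed model of the Statistical analysis paragraph. That paragraph is written in the past tense; if outcomes have already been analysed, report the adjusted model as a labelled sensitivity analysis.
- Reword the diet sentence in Workplan item 4 to say that all patients receive diet but may differ in how long they have had it, and that the analysis accounts for this.

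The cost is a record lookup and two degrees of freedom. No visit, procedure or patient is added.
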